#### Retrospective review:

In addition to the 40 patients prospectively enrolled and randomized, a retrospective review will be performed on all patients undergoing major lower limb amputation from July 2017 through December 2020. These patients will be identified through an Epic report with inclusion/exclusion criteria the same as the prospective portion, with the exception of refusal to participate as this portion will have a waiver of informed consent.

Patients with a regional nerve block will be compared to those without on age, gender, race, BMI, ASA class, length of operation, hospital length of stay, and oral and parenteral narcotic pain requirements.

**Statistical Analysis:** The two groups will be compared using descriptive statistics. Continuous data will be analyzed using student's t-test and/or Mann-Whitney U tests and categorical data will be analyzed using Chi square analysis.

**Sample Size:** We expect to include approximately 1000 patients in this study.

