### **Design of the study:**

#### Prospective enrollment:

This study was a double-blinded randomized controlled trial analyzing 40 patients undergoing major lower extremity amputation by the vascular surgery service at UCSF Fresno at Community Regional Medical Center, Clovis Community Medical Center, and Fresno Heart and Surgical Hospital. All included patients were evaluated by the vascular surgery service and had lower extremity amputation deemed necessary based on ischemic disease, infectious disease, and/or disfigurement. Patients were excluded if they were less than 18 years of age, pregnant, undergoing emergency amputations, staged amputations, or amputations by non-vascular surgeons, have known allergies to bupivacaine, are unable to communicate symptoms of pain, or refuse to participate in the study. Eligible patients were identified by the vascular surgery service in their private office or following a consultation by the vascular surgery service in the hospital. Upon identification, eligible patients or their surrogate decision maker were approached for consent by a member of the study team.

To randomize patients, consent forms were pre-labeled with a random subject identification number. This number served as the participants' study ID for all data collection in order to maintain privacy and confidentiality. Additionally, this number was linked to a sealed envelope containing the random treatment group. The study coordinator created the labels and assembled the envelopes to ensure all investigators remained blind to the treatment groups. This sealed envelope was given to the anesthesia providers, by the vascular surgery service, for the amputation. The anesthesia team then administered the assigned treatment prior to induction of general

anesthesia. Half of the patients were randomized into the treatment group, and half of the patients were randomized into the control group.

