Patients randomized to the treatment group received regional nerve blocks (sciatic and femoral) with bupivacaine at the dose of 1 mg/kg. The anesthesiologists are experts in pain management, and they are trained to perform regional nerve blocks. Femoral and sciatic nerve blocks are within their scope of practice, and they have been performing them quite frequently especially in orthopedic operations. Patients randomized to the control group received two needle sticks (in the sciatic and femoral distributions) with normal saline to maintain the double-blinded investigation. Because the injections are the standard of care, the appropriate billing codes already exist in Epic electronic medical record and are regularly used by the anesthesiologists. Therefore, for this study, the anesthesiologists ordered and documented the injections as normal.

The remainder of the operation and post-operative course proceeded per the standard of care. Post-operative pain was evaluated daily until discharge by the vascular surgery service using the McGill pain questionnaire. Additional data collected included age, gender, race, BMI, ASA class, length of operation, hospital length of stay, oral and parenteral narcotic pain requirements. Any adverse events were immediately reported to the Principal Investigator and the IRB. A Medical Monitor with suitable expertise was provided with study data every 3 months. The medical monitor used that data, especially the unforeseen adverse events and complications, to ensure the study safety. The patients were monitored while in the hospital and after discharge. The patients followed up per routine in vascular office, and pain along with other data was collected until six months after discharge.

Enrollment for the prospective portion is now closed and all patients have been discharged.

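### The retrospective block versus no-block comparison pools hospitals and 42 months with unadjusted tests, and hospital, operation date and anesthesiologist are not named as collected or analyzed

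*Combined protocol and SAP*

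**What the plan says.** The Prospective enrollment section places the randomized trial "at Community Regional Medical Center, Clovis Community Medical Center, and Fresno Heart and Surgical Hospital". The Retrospective review section then adds a non-randomized cohort: "a retrospective review will be performed on all patients undergoing major lower limb amputation from July 2017 through December 2020". That section names no hospitals, but it takes "inclusion/exclusion criteria the same as the prospective portion", apart from refusal to participate.

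Two passages list variables. For the prospective part: "Additional data collected included age, gender, race, BMI, ASA class, length of operation, hospital length of stay, oral and parenteral narcotic pain requirements". For the retrospective part: "Patients with a regional nerve block will be compared to those without on age, gender, race, BMI, ASA class, length of operation", followed by hospital stay and narcotic use. Neither list names hospital, operation date or anesthesiologist.

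The Statistical Analysis paragraph compares two groups with t-tests or Mann-Whitney tests for continuous data and chi-square tests for categorical data. It describes no stratification, regression, matching or weighting. The Sample Size paragraph expects about 1000 patients. If that total includes the 40 randomized patients, about 960 were not randomized to block or no block.

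**The concern.** In the retrospective cohort the block was given or withheld in routine care, and the protocol does not say how that was decided. Two of the outcomes in the hypothesis, length of stay and narcotic requirement, depend partly on when a unit discharges patients and how it orders analgesia. If a hospital or a period with more blocks also has shorter stays for unrelated reasons, a pooled comparison credits the block with the difference. If it has longer stays, the same mechanism hides a benefit.

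This gap is separate from the lack of patient-level adjustment. Age, gender, race, BMI, ASA class and length of operation do not record site or period, so a model built only on the listed covariates could not be relied on to remove the bias. The planned tests also have no place for site or period, even if the extract holds them.

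**Working it through.** **Figures in the documents.** July 2017 through December 2020 is 3 × 12 + (12 − 7) + 1 = 42 months, or 3.5 years. The 1000 cannot be re-derived, because no alpha, power, effect size, SD or block share is given. It is a statement of expected numbers.

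**Assumed inputs.** The documents give no block rate, SD or mean stay by hospital. The illustration takes 1000 patients, 700 at hospital A and 300 elsewhere; no true block effect; SD 6 days; mean stay differing by d = 1, 2 or 3 days between A and the rest; two-sided alpha 0.05. Block use is p₁ at A and p₂ elsewhere.

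**Formulas.**
- Block group: n₁ = 700p₁ + 300p₂. No-block group: n₀ = 1000 − n₁.
- Share of each group treated at A: s₁ = 700p₁/n₁ and s₀ = 700(1 − p₁)/n₀.
- Bias = d(s₁ − s₀).
- SE = 6√(1/n₁ + 1/n₀).
- Rejection probability = Φ(|bias|/SE − 1.96) + Φ(−|bias|/SE − 1.96).

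**Worked case, 50% versus 10%.** n₁ = 350 + 30 = 380 and n₀ = 350 + 270 = 620. s₁ − s₀ = 350/380 − 350/620 = 0.921 − 0.565 = 0.357. SE = 6√(1/380 + 1/620) = 0.39 days.

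| Block use, A vs rest | n₁ / n₀ | s₁ − s₀ | Bias in days, d = 1, 2, 3 | False-positive rate |
|---|---|---|---|---|
| 30% vs 30% | 300 / 700 | 0 | 0, 0, 0 | 5%, 5%, 5% |
| 40% vs 30% | 370 / 630 | 0.090 | 0.09, 0.18, 0.27 | 5.6%, 7.4%, 10.6% |
| 40% vs 20% | 340 / 660 | 0.187 | 0.19, 0.37, 0.56 | 7.5%, 15%, 29% |
| 50% vs 10% | 380 / 620 | 0.357 | 0.36, 0.71, 1.07 | 15%, 45%, 78% |

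At SD 8 days the last row becomes 11%, 28% and 54%. Adding the between-hospital variance to the SE moves the SD 6 figures by at most 1.4 percentage points (78.1% to 76.7%). The sign of the bias depends on which hospital has the longer stay.

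**Check by simulation.** Three hospitals with 50%, 30% and 20% of 1000 patients, normally distributed outcomes, no block effect, 3000 runs per scenario:

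| Block use by hospital | Span of hospital means | t-test | Mann-Whitney | Linear model with hospital terms |
|---|---|---|---|---|
| 30/30/30% | 0.3 SD | 5.1% | 5.2% | 5.1% |
| 40/30/20% | 0.3 SD | 8.3% | 8.2% | 4.6% |
| 60/30/10% | 0.3 SD | 31.7% | 30.8% | 4.9% |
| 60/30/10% | 0.5 SD | 69.5% | 68.7% | 4.9% |

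Choosing the rank test does not help. Including hospital in the model restores the nominal rate in these scenarios. The same algebra applies with calendar period in place of hospital.

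**The case against.** The strongest reply is that bias needs two conditions together, block use varying by hospital or period and stay or prescribing varying with it, and the documents give no data on either. All patients belong to one vascular surgery service, since amputations by other surgeons are excluded. A shared service may narrow differences in discharge and ordering. With equal block rates there is no bias at all. This stands: the size is unknown, and near zero is within the range.

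A reader might also infer several stronger things that the text does not support.

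- **That block use is shown to depend on the operator.** The protocol says of the anesthesiologists that "they have been performing them quite frequently especially in orthopedic operations", but this describes them as a group, and the remark concerns other operations. It shows no variation between operators. The number of anesthesiologists is not given, only the plural.
- **That hospital and date will not be collected.** The retrospective list states what the groups are compared on, and the prospective list need not be exhaustive. Operation date must be available to apply the window, and admission and discharge dates to derive stay. The supportable statement is that these items are not named as collected or analyzed.
- **That standard errors are too narrow because patients cluster by anesthesiologist.** This requires both outcomes and block use to cluster by anesthesiologist, and neither is documented.
- **That the randomized comparison is affected.** Randomization protects the 40 patients in expectation, although no stratification by hospital is described.

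Finally, the plan adjusts for nothing, so this could be seen as one part of a general confounding problem. That is fair, but adding only the listed covariates would still leave site and period out.

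**Conclusion.** The point stands for the retrospective comparison. As written, the plan could report a hospital or calendar difference as a block effect, and a reader of the results could not tell the two apart. The size cannot be established from the documents. Under the assumed inputs the false-positive rate runs from the nominal 5% to 78%, driven mainly by how far block use differs between hospitals. The upper end rests on a strong contrast of 50% versus 10%, and the moderate contrasts give about 6–29%. The conclusion rests on one inference, that the retrospective cohort spans the three hospitals, and on the plausible but undocumented premise that practice varies by site or year. It is worth correcting because the retrospective patients make up nearly all of the expected sample and the review is described as still to be done.

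**What to change.** - Add hospital to the Epic report, and keep operation date as an analysis variable.
- State that the main retrospective comparison of stay and narcotic use is made within hospital and calendar year, by strata or fixed effects, alongside the listed baseline covariates.
- Tabulate block use by hospital and year, so that readers can see whether the first condition for bias is met.
- Optionally, add a coded anesthesiologist ID and report anesthesiologist-clustered standard errors as a sensitivity analysis, provided there are enough clusters. With few clusters such errors can be unreliable.

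The cost is one additional structured field (two with the anesthesiologist ID) and a sentence or two in the Statistical Analysis paragraph. Hospital-years in which all or no patients had a block contribute nothing to the within-stratum comparison, and confidence intervals may be somewhat wider. The 40 randomized patients need no change on this account, and no patient's care is affected.

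### The retrospective block versus no-block comparison (about 96% of patients) is not randomised, but length of stay and narcotic use are to be tested without adjustment

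*Combined protocol and SAP*

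**What the plan says.** The Retrospective review section adds a chart review to the 40 randomised patients: "a retrospective review will be performed on all patients undergoing major lower limb amputation from July 2017 through December 2020". Its groups are formed by whether a block was given: "Patients with a regional nerve block will be compared to those without on age, gender, race, BMI, ASA class, length of operation". The same list goes on to hospital length of stay and to oral and parenteral narcotic requirements, so patient characteristics and outcomes are treated alike.

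The Statistical Analysis paragraph is two sentences long. It opens with "The two groups will be compared using descriptive statistics", then names the t-test and/or Mann-Whitney U test for continuous data, and ends with "categorical data will be analyzed using Chi square analysis". Regression, matching, stratification and weighting are not mentioned anywhere. The Sample Size paragraph gives one total of about 1000 for the study.

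The Specific Aims set one aim for the whole study: to find out whether blocks improve pain control and reduce length of stay and narcotic requirements. The Background calls the block part of usual care and gives no rule for who receives it.

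For the trial patients, the Prospective enrollment section says: "Half of the patients were randomized into the treatment group". It adds "Patients randomized to the control group received two needle sticks (in the sciatic and femoral distributions) with normal saline", and that "the anesthesiologists ordered and documented the injections as normal".

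**The concern.** Randomisation protects the comparison among the 40 trial patients. It does not protect the comparison among the other 960 or so. If clinicians gave blocks more often to sicker patients, or to fitter ones, an unadjusted test mixes the block with the differences between the patients who did and did not receive it. That can create, hide or exaggerate a difference in stay or narcotic use. Tabulating age or ASA class by group would show an imbalance but would not correct the outcome comparison for it. A larger sample does not remove such a bias; it makes a spurious difference more likely to reach significance.

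Two gaps are linked to this.

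- The plan does not say which two groups its single analysis paragraph refers to. Nothing keeps the randomised patients apart from the review, and pooling would mix the randomised contrast with the confounded one.
- The review takes all amputations in a calendar window, and no step checks whether trial participants fall in it. If they do, a saline control whose injection was ordered and documented in the usual way might be read as a block.

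**Working it through.** **Share of patients affected.** The Sample Size paragraph gives about 1000 and the Retrospective review section gives 40 randomised. If the 1000 includes the 40: (1000 − 40)/1000 = 96.0%. If it does not: 1000/1040 = 96.2%. The total is approximate and has no derivation. For totals of 900 to 1100 that include the 40, the share is 860/900 = 95.6% to 1060/1100 = 96.4%.

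**Possible size of the bias.** The documents give no block rate, no covariate distribution and no spread for length of stay. Every input here is therefore an assumption: N = 960; 40% of patients in ASA class 4; residual SD of log stay 0.7; ASA class the only confounder; no true block effect; two-sided 5% test.

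Formulas:

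- Bias in log stay = ln(stay ratio, ASA 4 versus others) × [P(ASA 4 | block) − P(ASA 4 | no block)]
- SE² = v₁/n₁ + v₀/n₀, where v = 0.7² + ln(stay ratio)² × q(1 − q), and q is the ASA 4 share in that group
- False-positive rate = Φ(|bias|/SE − 1.96) + Φ(−|bias|/SE − 1.96)

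Middle case (blocks given to 40% of ASA 4 patients and 20% of others; ASA 4 stays 30% longer):

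- Overall block rate = 0.4 × 0.4 + 0.6 × 0.2 = 0.28, so n₁ = 268.8 and n₀ = 691.2
- P(ASA 4 | block) = 0.16/0.28 = 0.571; P(ASA 4 | no block) = 0.24/0.72 = 0.333
- Bias = ln(1.30) × 0.238 = 0.0625, a stay ratio of 1.06
- SE = 0.0512, bias/SE = 1.22, false-positive rate = 23.1%

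All four cases:

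| Block use, ASA 4 vs others | ASA 4 stay | Bias (log) | SE | Unadjusted ratio (expected 95% interval) | False positives |
|---|---|---|---|---|---|
| 30% vs 20% | +15% | 0.0184 | 0.0532 | 1.02 (0.92 to 1.13) | 6.4% |
| 40% vs 20% | +30% | 0.0625 | 0.0512 | 1.06 (0.96 to 1.18) | 23.1% |
| 50% vs 20% | +50% | 0.1342 | 0.0502 | 1.14 (1.04 to 1.26) | 76.1% |
| 20% vs 40% | +30% | −0.0579 | 0.0491 | 0.94 (0.86 to 1.04) | 21.8% |

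With N = 1000 the middle case gives 23.8%. In simulation (5000 replicates) Mann-Whitney behaves like the t-test (6.0%, 22.4%, 75.2%, 20.9%), so choosing between them does not help. Adjusting for ASA class returns 4.4% to 5.1% and a ratio of 1.00.

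**What adjustment leaves behind.** Add to the middle case an unmeasured factor present in 30% of patients, with 10 to 15 points more block use and 20 to 30% longer stay. The adjusted ratio is then 1.02 to 1.04 and the false-positive rate 7% to 12%, against 34% to 48% unadjusted (simulation, assumed inputs).

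**Precision cost.** If covariates explain a share R² of block use, and none of the outcome, the standard error grows by 1/√(1 − R²): 1.12 at R² = 0.2, 1.20 at 0.3 and 1.29 at 0.4. In simulation the five listed covariates alone changed it by −2% to +1%. Adding amputation level, hospital and year widened it by 0% to 29% as R² rose from 0.06 to 0.42.

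**The case against.** **The plan calls the comparison descriptive.** It does, but hypothesis tests follow in the next sentence, and the study's only aim is worded as an effect. No section limits the retrospective part to association. An association-only label would remove much of the risk of misreading. It would still leave unused the adjustment variables already collected.

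**The size is speculative.** This stands. The documents do not say how blocks were chosen. The illustration runs from nearly nominal to severe, and it covers length of stay only; narcotic use is not illustrated. A reader might infer that the retrospective result will be biased, or biased in favour of the block. The documents support neither.

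**The exclusions reduce the problem.** Emergency and staged amputations are excluded. This may help, but nothing links urgency or staging to block use, so no credit can be assigned.

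**The trial patients are already separate.** The wording about a review in addition to the 40, and the separate identification arrangements under Confidentiality and Privacy, suggest distinct groups. A reader might infer that saline controls will be counted as blocks. That would require enrolment inside the window (dates are not given), no exclusion step, block status taken from orders or billing (not stated), and saline not recognisable in the record. It is a point to check, not an established error.

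**Hospital adjustment is presumed.** The three sites, "Community Regional Medical Center, Clovis Community Medical Center, and Fresno Heart and Surgical Hospital", are named for the prospective part only. Hospital is therefore proposed only if it can be retrieved.

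**Conclusion.** The concern holds and should be fixed. For about 96% of patients, the plan tests length of stay and narcotic requirements between groups that were not randomised, with no adjustment, under an aim worded as an effect. Any imbalance in age, gender, race, BMI or ASA class goes straight into those results. The direction and size are unknown: under the assumptions above, the false-positive rate for length of stay is about 6% to 76%, with expected ratios of 0.94 to 1.14 when the truth is 1.00.

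It would go too far to say that the randomised comparison is compromised, and also to say that it is safe. It is unaffected only if the 40 are analysed apart from the review, and the Statistical Analysis paragraph does not say so. Nor would adjustment make the retrospective estimate causal, since factors such as preoperative pain or opioid use are not listed.

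**What to change.** 1. Analyse and report the 40 randomised patients separately from the retrospective cohort, and define the groups in each analysis.
2. Check whether any trial participants appear in the Epic report, and remove them before groups are formed. No section says that Epic holds the study ID, so this needs the separately stored key described under Confidentiality and Privacy.
3. For length of stay, and for oral and parenteral narcotic requirements, prespecify a regression on block status adjusted for age, gender, race, BMI and ASA class. A linear model for log stay, and a log-link model with robust standard errors for dose (which allows zero doses), would serve; other valid models are possible.
4. Add amputation level, hospital and calendar year if they can be retrieved and if overlap between groups is adequate. Check overlap before fitting, above all by hospital and year.
5. Leave length of operation out of the main model, because it is not a baseline variable.
6. State how in-hospital deaths are handled for length of stay, since a death shortens the stay.
7. Keep the planned unadjusted tests for the descriptive table, and report the retrospective result as an association with possible residual confounding.

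The cost is about a paragraph of analysis text, one linkage step, up to three extra fields and modest analyst time. Some precision is lost if the covariates strongly predict block use. If blocks were concentrated in one hospital or period, poor overlap could limit the estimate to part of the cohort.

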Regional nerve block is part of usual care and may serve as adjuncts for pain control after major lower extremity amputations. This pain control may be achieved by injecting bupivacaine into the sciatic and femoral nerves. Bupivacaine is an amide-type local anesthetic approved by the Food and Drug Administration (FDA) for local or regional anesthesia or analgesia for surgery. The dosage approved by the FDA for peripheral nerve blocks are 0.25% and 0.5%. The potential risks are central nervous system and cardiovascular system reactions. The central nervous system reactions are characterized by restlessness, anxiety, dizziness, or tremors. The cardiovascular system reactions are characterized by decreased cardiac output, heart block, hypotension, bradycardia, or arrhythmia. These risks are small and can be minimized further by slow administration and aspiration prior to administration to avoid intravascular injection. Other rare but potential risks of regional nerve block are nerve injury and hematoma formation.

Although bupivacaine is widely used for pain control, there are very few studies looking at regional nerve blocks as adjuncts for pain control after major lower extremity amputations. The number of randomized controlled trials is even fewer and none have been conducted in the United States. Baddoo looked at ten patients undergoing major lower extremity amputations (nine above knee amputations and one below knee amputation) with regional nerve blocks (a sciatic nerve block combined with either a 3-in-1 block or a psoas compartment lumbar plexus block). All ten patients were

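### The non-randomised block versus no-block cohort is given only unadjusted tests, and no rule keeps it apart from the 40 randomised patients

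*Combined protocol and SAP*

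**What the plan says.** The protocol contains two designs. Under Design of the study, Prospective enrollment, 40 patients were randomised to a bupivacaine block or to saline injections at the same two sites: "Half of the patients were randomized into the treatment group, and half of the patients were randomized into the control group". Enrolment is closed and all patients have been discharged.

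Under Retrospective review, a second part covers July 2017 to December 2020: "In addition to the 40 patients prospectively enrolled and randomized, a retrospective review will be performed". Its comparison is by block status: "Patients with a regional nerve block will be compared to those without on age, gender, race, BMI, ASA class", and the list continues with length of operation, length of stay and narcotic use. Block was not assigned by the study here. Background and Significance says: "Regional nerve block is part of usual care and may serve as adjuncts for pain control after major lower extremity amputations".

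One Statistical Analysis paragraph follows. It opens with "The two groups will be compared using descriptive statistics" and names Student's t-test and/or "Mann-Whitney U tests and categorical data will be analyzed using Chi square analysis". The Sample Size entry is a single sentence: "We expect to include approximately 1000 patients in this study".

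Pain is described only for the prospective patients: "Post-operative pain was evaluated daily until discharge by the vascular surgery service using the McGill pain questionnaire". It is not in the cohort's list of variables.

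**The concern.** Narcotic requirements and length of stay are two of the three outcomes in the Hypothesis, and Specific Aims asks whether blocks improve them. In the cohort, patients had a block or not as part of usual care, so those with a block may differ from those without in ways that affect both outcomes. The plan lists age, gender, race, BMI and ASA class as things to compare, not as covariates, and names no regression, matching, weighting or stratification. A difference found this way mixes any effect of the block with differences between the patients. The documents do not say who received blocks at these hospitals, so the error could create a false benefit or could hide or reverse a real one.

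The second gap is that the paragraph does not say which two groups it means or whether the two parts are combined. The sham-controlled randomised comparison is the only one protected from confounding. If it were pooled with the cohort, that protection would be lost.

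**Working it through.** **The text.** The words about the two groups can be taken in at least these ways:

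| Reading | Randomised trial | Cohort |
|---|---|---|
| Each part separately | has its own tests | unadjusted |
| Randomised arms only | has its own tests | no stated test |
| Cohort only | no stated analysis | unadjusted |
| Both parts pooled by block status | none of its own | unadjusted, mixed in |
| Prospective versus retrospective | none of its own | block not compared |

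No reading gives the cohort an adjusted analysis. That part of the point does not depend on which reading was meant.

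**Share of randomised patients if pooled.** If the 1000 includes the 40: 40/1000 = 4.0%, leaving 960/1000 = 96.0% non-randomised. If the 40 are extra: 40/1040 = 3.8%, leaving 96.2%.

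**Illustration of unadjusted testing.** There is no plan figure to reproduce: the documents give no alpha, power, effect size, SD, block share or split of the 1000. Assumptions: two-sided 5%, N = 960 cohort patients (1000 − 40), block share p from 10% to 50%, no true effect, and a non-causal difference of b SD.

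- SE = 1/√(N·p·(1−p))
- Rejection rate = P(Z > 1.96 − b/SE) + P(Z < −1.96 − b/SE)

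| p | SE | b = 0.10: total | side of the bias | other side | b = 0.05: total |
|---|---|---|---|---|---|
| 0.1 | 0.108 | 15.3% | 15.1% | 0.19% | 7.5% |
| 0.3 | 0.070 | 29.5% | 29.5% | 0.04% | 10.9% |
| 0.5 | 0.065 | 34.1% | 34.1% | 0.02% | 12.1% |

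Example for p = 0.1: SE = 1/√86.4 = 0.108 and b/SE = 0.93, so the upper tail is P(Z > 1.03) = 15.1%. Without bias each side would be 2.5%. At b = 0.10 the range is 15.8% to 35.3% with N = 1000 and 10.3% to 20.1% with N = 500.

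**What adjustment can do.** Treat the SE as unchanged, with N = 960 and b = 0.10. If adjustment removes half the bias (b = 0.05 left), the rate is 7.5% to 12.1%. If it removes 80% (b = 0.02 left), it is 5.4% to 6.1%. The gain depends on how much of the bias the covariates capture.

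**What pooling does.** Add 20 + 20 trial patients whose mean equals the cohort's overall mean, c·p, where c is the cohort shift. The pooled difference is (n₁c + 20cp)/(n₁ + 20) − 20cp/(n₀ + 20), with n₁ = 960p and n₀ = 960 − n₁. For c = 0.10 this is 0.084 SD at p = 0.1 and 0.096 SD at p = 0.5. The rejection rates (noncentral t) are 13.6% and 32.9%. Forty randomised patients barely dilute the bias.

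**Pain.** With one value per patient, 20 per arm and complete data, the 95% CI half-width is t(0.975, 38)·√(2/20) = 0.640 SD. The 1000 has no bearing on this outcome.

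**The case against.** **The parts may already be meant to stand apart.** The retrospective review is introduced as additional to the 40, the parts have their own design headings, and Confidentiality and Privacy handles consent and identifiers separately. A reader might infer that the trial has been left without an analysis, or that the plan intends to pool. The documents do not support either: comparing block with no block within each part is the more natural reading, and on it two-sample tests suit the randomised patients. This objection largely stands. What remains is that no sentence states it and that one undivided figure of about 1000 leaves pooling open. On the trial side this is a request for clarification.

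**The comparison is called descriptive.** A descriptive table needs no adjustment. But the same paragraph names hypothesis tests, and the aims are about effect.

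**The rejection rates rest on chosen inputs.** Correct. Bias and block share are assumed, and the normal-theory rate does not represent the Mann-Whitney option. A reader might take 15% to 34% as this study's false-positive rate; the documents give no basis for that.

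**Overlap is not shown.** Trial injections, sham included, were documented as normal injections, and the cohort comes from an Epic report on all amputees in its window. A reader might infer that sham patients will be counted as blocked. No trial enrolment dates are given, so overlap is possible but not established.

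**Conclusion.** The point holds for the cohort and must be fixed before that analysis is run: as written, differences in length of stay and narcotic use between patients with and without a block cannot be attributed to the block. This follows from the text alone, since allocation was not random and only unadjusted tests are named, and it needs none of the assumed figures. Those figures show only that a small non-causal difference could matter in a cohort of this size; they say nothing about its actual size or direction.

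The lack of a pooling rule is a smaller matter. Pooling is not the likely intention, but it is not excluded, and a pooled result would be about 96% non-randomised. Pain, the first-named outcome, rests on at most 40 patients (20 per arm), whatever the total.

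**What to change.** 1. **Cohort.** Analyse it separately, labelled observational, for length of stay and narcotic use, by regression of each outcome on block status with age, gender, race, BMI and ASA class. Use a form suited to skewed outcomes, for example the log scale with a stated rule for zero narcotic totals. Say whether oral and parenteral narcotics are one outcome or two. Show the unadjusted result beside the adjusted one, and state that residual confounding remains; amputation level and indication, for example, are not in the listed data.
2. **Trial.** State that the 40 randomised patients are analysed on their own by assigned arm, with estimates and 95% CIs, and are not pooled with the cohort. Disclose that this was specified after enrolment closed and all patients were discharged. The named two-sample tests are acceptable where there is one value per patient. Pain was scored daily in hospital and collected to six months after discharge, so a single pain summary must be fixed before analysis.
3. **Overlap.** As a precaution, check the Epic list against the separately stored study key and remove any of the 40.
4. **Sample size.** State N by part and outcome: the roughly 1000 applies only to length of stay and narcotic use, and pain has at most 40 (20 per arm). Say whether the 1000 includes the 40.

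The cost is a few sentences, one regression per cohort outcome and one list check. No new patients are needed, and the five covariates are already collected. The downsides are slightly more analysis work, a possibly weaker cohort result, a less favourable stated N for pain, and confounding that these covariates cannot fully remove.
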